⁵ Maths students have one additional exam, and therefore receive an additional reminder text.

about the requirements for participating colleges. College leaders were asked to give their consent and return a signed copy of the MOU to the developer.

Students were recruited to the intervention in September and October 2017 using an online survey provided to college 'project leads' by the Behavioural Insights Team. The survey included information about 'Texting Students and Study Supporters' ('Project SUCCESS') and what would be expected of participants, so that they were able to give informed consent. The survey also included a small number of questions about students' attitudes towards learning and their motivation to study. Students willing to take part were asked to nominate a named study supporter, describe their relationship and provide their study supporters' contact details. Study supporters were not asked to give their consent to take part in the trial, but were able to opt-out of the intervention when the first text message was sent (in early November 2017).

TRIAL DESIGN/ DESCRIPTION OF TRIAL ARMS

Project SUCCESS is being evaluated using a four-armed cluster randomised controlled trial (RCT) with randomisation to each of the four trial arms at the individual level. Clustering within colleges will be accounted for as a fixed effect in the model. The four arms of the trial are:

- Student receives text messages
- Study supporter receives text messages
- Student and study supporter receive text messages
- Control (no text messages)

SAMPLE SIZE

The trial is being conducted in 31 FE colleges.⁶ An average of 123 eligible students per college have given their informed consent to participate in the trial; a total of 3,823 individuals. Students retaking both maths and English have been assigned at random to either the maths or English strand of the intervention, so that approximately 50 per cent are participating in each stand.

NUMBER AND TIMING OF MEASUREMENT POINTS

There will be a single post-intervention measurement point. GCSE resit attainment in maths and English post-treatment will be taken from the National Pupil Database (NPD) in autumn 2018 for all students who participated in the programme in the 2017/18 academic year. Students retaking both English and maths will be randomly assigned to receive texts about just one of these subjects and the primary outcome will be attainment in the subject the student received texts about.

Randomisation

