- We assume a total of 31 participating colleges and an average of 60 students per college for each of the three pairwise comparisons, with 30 in each treatment arm and 30 in the control (with a broadly even split between maths and English). This means a total of 930 students in each treatment arm and 930 in the control group; a total of 1860 for each of the three pairwise comparisons.
- Maths and English outcomes (i.e. a pass or fail in the English or maths GCSE resit exam) will be considered together as a single outcome variable.
- We assume equal proportions of students in the treatment and control groups ($P = 0.5$) for each pairwise comparison.
- We anticipate a baseline pass rate of 30% ($\theta = 0.3$)
- We have three separate significance tests for the primary outcome, with each of the three treatment groups separately compared to the control group.
- We assume a nominal Type 1 error rate of 0.05 with a two-tailed test, amended using a Bonferroni adjustment for three separate independent tests, to a value of 0.0167 for each test. The Type II error rate is set at 0.2, giving power of 0.8.
- We assume¹⁴ an intra-cluster correlation coefficient (ρ) of 0.1.
- No between site heterogeneity is expected (i.e. $\omega = 0$).
- No level 1 baseline test covariate has been included in the calculation, for reasons explained below. There are also no level 2 stratification variables because we have treated the colleges as random effects and no preliminary stratification was undertaken for college type.
- We assume no attrition in the design, our rationale for which is explained below.
- The EverFSM MDE calculation combined all three treatment arms and assumed a 20% prevalence per college, giving $(90 \times 0.2) + (30 \times 0.2) = 24$ students per college.

The assumptions for each MDE estimation are given in Table 2, below.

The sample size calculations in Table 2 were originally intended to enable the detection of a seven percentage point increase in the GCSE pass rate, from (an estimated) 30 per cent to 37 per cent.¹⁵ However, the underlying model for the purposes of this power calculation, which we have now changed as described above, assumed, a fixed effects model, with no random variation at Level 2, i.e. colleges represented strata from a population fully defined by the sample.

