$$\text{logit}(\pi)_{ij} = \beta_{0j} + \beta_{1j}\text{treatment}_{ij} + r_j \text{ (Treatment = Student and Supporter text jointly)}$$

Subgroup analyses

We will approach the analysis for students who have ever been eligible for Free School Meals (EverFSM) in two ways. First, we will combine all treatment groups into a single treatment group and then subset to include only those who have ever had free school meals, as recorded on the NPD (EverFSM). Secondly, Model (2) will be extended through the inclusion of a dummy variable for FSM recipients (variable = EverFSM) and a corresponding interaction effect between FSM and treatment to test for a differential impact on FSM recipients. The specifications are:

$$\text{logit}(\pi)_{ij} = \beta_{0j} + \beta_{1j}\text{treatment}_{ij} + r_j \text{ (Domain = EverFSM, Treatment = All groups combined)}$$

$$\text{logit}(\pi)_{ij} = \beta_{0j} + \beta_{1ij}\text{treatment}_{ij} + \beta_{2ij}\text{EverFSM}_{ij} + \beta_{3ij}\text{EverFSM}.\text{treatment}_{ij} + r_j \text{ (Treatment = All groups combined)}$$

As proposed in the protocol, we will also explore whether there is evidence for a differential effect on maths and English outcomes, gender and sitting either English or maths versus sitting both English and maths:

$$\text{logit}(\pi)_{ij} = \beta_{0j} + \beta_{1ij}\text{treatment}_{ij} + \beta_{2ij}\text{Subject}_{ij} + \beta_{3ij}\text{Subject}.\text{treatment}_{ij} + r_j \text{ (Treatment = All groups combined)}$$

$$\text{logit}(\pi)_{ij} = \beta_{0j} + \beta_{1ij}\text{treatment}_{ij} + \beta_{2ij}\text{Gender}_{ij} + \beta_{3ij}\text{Gender}.\text{treatment}_{ij} + r_j \text{ (Treatment = All groups combined)}$$

$$\text{logit}(\pi)_{ij} = \beta_{0j} + \beta_{1ij}\text{treatment}_{ij} + \beta_{2ij}\text{N_Subjects}_{ij} + \beta_{3ij}\text{N_Subjects}.\text{treatment}_{ij} + r_j \text{ (Treatment = All groups combined)}$$

Effect size calculation

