The EEF guidance suggests the use of a relative risk ratio (RR) as an effect size for binary outcomes. Consequently, this is what we propose to use here for each of the three models making up our primary outcomes. We note that the primary outcome models proposed here are relatively simple and do not include controls for covariates. This is advantageous given that the RR can vary conditional upon covariate levels and would require the centring of covariates in the logistic model to assess the RR at its average covariate value. However, we do not have this issue with the models proposed here, but the Level 2 random college effect will translate into the odds for students at the average level of success across colleges.

The protocol did not specify the calculation of effect sizes for the primary outcomes but did propose an effect size appropriate to continuous outcomes for class attendance. As noted above, we now propose to treat the model for class attendance using a binomial distribution appropriate to modelling differences in proportions. We therefore propose to use the relative risk ratio as a measure of the effect size for this outcome

We will calculate the relative risk ratio, following a method outlined by Fleiss & Berlin (2009),³⁰ as the measure of effect size, using the results, as appropriate, from the three versions of model (2) above for each of the treatment groups and for the class attendance model.

$$RR = \frac{1 + \exp^{-\alpha}}{1 + \exp^{-\alpha - \beta}} \quad (5)$$

In (5) above α refers to the constant from the logistic model (2) and β refers to the treatment indicator.

³⁰ Cooper, H., Hedges, L. and Valentine, J. *The handbook of research synthesis and meta-analysis*

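### That the RR varies with covariates is a limit of formula (5), not a reason to leave subject, number of resits, gender and EverFSM out of the primary and attendance models

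*SAP*

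**What the plan says.** Model (2), under Primary intention-to-treat (ITT) analysis, contains a treatment indicator and a random college intercept and nothing else. The attendance models take the same form. Under Effect size calculation the SAP remarks that the primary models "do not include controls for covariates. This is advantageous given that the RR can vary conditional upon covariate levels", and adds that covariates would have to be centred before the RR could be read off. The RR is then obtained from formula (5), using the constant and the treatment coefficient.

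The reason given for not adjusting lies elsewhere. The ITT section says baseline attainment data are lacking. Footnote 17 explains that college assessment scores exist for very few students, that prior GCSE grades would vary little, and that raw marks cannot be obtained.

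Other baseline variables are mentioned:

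- **Survey items.** The recruitment survey, run in September and October 2017, included a few questions on "attitudes towards learning and their motivation to study". Randomisation followed at the end of October. The Secondary outcomes section assigns attitude data to the process evaluation.
- **Subject.** The Randomisation section says up to 100 randomisations were allowed in order to balance on it.
- **Subgroup variables.** The subgroup models include EverFSM, and also look at maths versus English, "gender and sitting either English or maths versus sitting both English and maths".
- **NPD variables.** Those that predict allocation significantly enter a sensitivity version of model (2).

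**The concern.** An RR that changes with covariate values is a property of the plug-in formula, not of adjusted analysis. If the remark is taken as justification, the primary and attendance models forgo pre-treatment variables that may predict passing, turning up for the exam (no-shows count as fails) or attending class. The SAP gives no reason for leaving these variables out, because its attainment argument does not touch them. At stake is some precision in a trial whose sample is fixed and whose MDE of 6.8 points lies close to its target of 7. The effect size is affected too: formula (5) yields no pass-rate difference, which the SAP also promises to report, and its RR refers to a college of average success.

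**Working it through.** **1. Reproduce the stated MDE.** The inputs are all from Calculation of sample size:

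- "We assume a nominal Type 1 error rate of 0.05 with a two-tailed test", adjusted "to a value of 0.0167 for each test. The Type II error rate is set at 0.2, giving power of 0.8"
- "We assume a total of 31 participating colleges and an average of 60 students per college", so 31 × 60 = 1,860 per comparison
- "We assume equal proportions of students in the treatment and control groups", so P = 0.5
- "We anticipate a baseline pass rate of 30" per cent, so σ = √(0.3 × 0.7) = 0.458
- ρ = 0.1, ω = 0, no attrition and no covariates

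With ω = 0, formula (1) on the percentage-point scale is

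MDE = 100 × σ × M × √[(1 − ρ)(1 − R₁²) / (P(1 − P)Jn)].

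With 30 degrees of freedom M = 3.389, and with R₁² = 0

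MDE = 100 × 0.458 × 3.389 × √(0.9/465) = 6.83, against the stated 6.8.

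The same method gives 10.66 for EverFSM, against the stated 10.7.

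**2. Add covariates.** The document gives no R₁², so a range is assumed. The MDE scales by √(1 − R₁²), and the equivalent sample size by 1/(1 − R₁²).

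| Assumed R₁² | MDE (points) | Power for 6.8 points | Equivalent sample |
|---|---|---|---|
| 0 | 6.83 | 0.80 | 1.00 |
| 0.02 | 6.76 | 0.81 | 1.02 |
| 0.05 | 6.66 | 0.82 | 1.05 |
| 0.10 | 6.48 | 0.84 | 1.11 |

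Formula (1) works on the linear scale, so these figures are approximate for a logistic model.

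**3. How strong must a covariate be?** Within-college variance is about 0.21 × 0.9 = 0.189. A 50/50 binary predictor with a pass-rate gap g has R₁² = (g/2)²/0.189. Reaching 2%, 5% or 10% therefore needs a gap of about 12, 19 or 27 points. Subject splits almost evenly (1,912 English, 1,911 maths). With an assumed gap of 10 points it gives 0.0025/0.189 = 0.013 and an MDE of 6.83 × √0.987 = 6.79.

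**4. Does the RR need a covariate-free model?** Take control and treatment pass rates of 30% and 37% at the covariate mean, and an assumed covariate SD of 0.6 on the logit scale. Formula (5) gives 1.23 at the mean, 1.18 at +1 SD and 1.28 at −1 SD. Averaging predicted probabilities over the covariate distribution, under treatment and under control, gives a single RR of 1.21.

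**5. Does omitting covariates avoid the difficulty?** Not fully. If the ICC of 0.1 is read on the latent logit scale (an assumption), the college SD is √[(0.1/0.9) × π²/3] = 0.605. Formula (5) then gives 1.233 for the average college, against 1.211 averaged over colleges. The SAP itself notes that the result refers to the average college. Its primary outcome, however, is the proportion passing among all who started.

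**6. Does the planned sensitivity model fill the gap?** It selects NPD variables by significant chance imbalance, not by relation to outcome, so the covariate list is unknown in advance. Once covariates enter, formula (5) gives the RR at whatever covariate values the constant represents, so averaged predictions would be needed there as well.

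**The case against.** The strongest reply is that the SAP does not choose an unadjusted model because of the RR. It gives lack of usable attainment data as the reason, and the RR remark comments on models already set. That stands. A reader might infer that the plan rejects all covariates on RR grounds. The documents do not support this: covariates appear in the imbalance sensitivity model and in the interaction models, and the SAP itself names centring as a way to handle them. What remains is that the attainment reason says nothing about subject, number of resits, gender or EverFSM.

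A reader might also infer that baseline data held on every student are being wasted. That is not shown. The NPD variables come with a later extract. The SAP does not say that every student answered the attitude questions or that the evaluator can link them. Footnote 21 concerns telephone numbers. The attitude data do have a planned use, in the process evaluation.

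Third, the gain is small. Randomised numbers average 3,823/2 ≈ 1,912 per comparison, which alone gives 6.83 × √(1860/1912) = 6.74 points, slightly more than covariates with an R-squared of 2% would deliver. The 7-point target is met without adjustment. This stands too, and it limits the weight of the point without removing it, since adjustment costs only a few coefficients among about 1,912 students.

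**Conclusion.** The point holds as a recommended improvement. The RR remark does not support an unadjusted model, and the SAP offers no other reason for omitting four variables it already plans to model. The size is modest and cannot be settled from the document: an MDE of 6.76 to 6.48 points, against 6.83, under an assumed R-squared of 2% to 10%. With weak predictors the gain is negligible, and the upper end would need strong ones. The benefit for attendance is not quantified.

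It would be wrong to conclude that the planned analysis is biased or misses its target. Unadjusted ITT in an individually randomised trial stratified by college is valid. The gap between 1.233 and 1.211 rests on reading the ICC on the latent scale. It reflects a choice between the RR for an average college and the RR for the whole sample, and does not show an invalid test.

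**What to change.** Before outcome data arrive in autumn 2018:

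- State that the primary and attendance models adjust for subject, one versus two resits, gender and EverFSM. Add the pre-randomisation attitude and motivation items if they can be linked.
- Code missing covariate values as a separate category, as footnote 23 already does for the missingness model.
- Replace formula (5) with the ratio and the difference of predicted probabilities under treatment and control, averaged over students and over the college effect, with delta-method or bootstrap intervals.
- Keep the unadjusted model as a sensitivity analysis, and delete the statement that having no covariates is an advantage.

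The cost is a revision of the SAP wording, some extra linkage work if the survey items are used, and the need to fix the model in advance. No new data collection is needed.
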